15.3 Fatal Overdose

We will collect data on fatal opioid overdoses using medical chart record review at 24 weeks for participants who are lost to follow-up. We will supplement this with information from contacts with persons listed on the participant's locator form when participants are lost to follow-up throughout the study. If a fatal opioid overdose occurred, the event also should be captured on the AE/SAE CRF.

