Yet little is known about XR-NTX implementation in U.S. office-based settings, and the FDA's decision has been criticized insofar as (1) the FDA "accepted a single trial of injectable naltrexone in Russia, unpublished at the time, as primary evidence of efficacy," and (2) "the study did not adequately assess risk of post-treatment overdose" [56]. Because agonist therapy is prohibited in Russia, these authors question the use of these data to gain approval in the USA where methadone and buprenorphine are widely available. Regardless of the merit of these concerns, the data from the Russian placebo-controlled efficacy trial do not directly address the effectiveness, implementation issues, safety, and costs of XR-NTX in U.S. HIV-infected populations.

Naltrexone for Treatment of Comorbid Alcohol Use Disorder. The CTN-0055 CHOICES pilot study demonstrated that 16% of participants with opioid use disorder had comorbid alcohol use disorder. Oral naltrexone received FDA approval in 1994 for treatment of alcohol use disorders and systematic reviews support its efficacy compared to placebo [57-61]; however, its success is limited by suboptimal adherence to daily dosing requirements [62, 63]. XR-NTX, which lasts 28 days, has improved response rates in alcohol-dependent patients. In a 6-month, multicenter trial of XR-NTX for alcohol dependence, those randomized to receive 380mg XR-NTX experienced a 25% greater decrease in heavy drinking day event rate compared to placebo [64], improved quality of life [65], and decreased holiday drinking [66]. In a post-hoc analysis limited to those with higher severity alcohol dependence, XR-NTX reduced heavy drinking days by 37% and compared with a 27% reduction for placebo-treated participants' improved maintenance of abstinence [67]. Treatment responses were highest among participants with at least 4 days of voluntary alcohol abstinence prior to their first dose of XR-NTX [64, 68], and were rapid in onset, with significant reductions in alcohol use observed after only 2 days [69]. XR-NTX did not significantly increase counseling or support group participation [69].

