4.1.1 Figure 2. Conceptual Model

4.2 Naltrexone (NTX) and Extended-Release Naltrexone (XR-NTX)

NTX is a potent opioid antagonist with high affinity for the mu-opioid receptor. In the U.S., it is approved for use in treating opioid dependence and alcohol dependence. It is highly efficacious in preventing relapse to opioid dependence provided that it is taken as prescribed, but adherence with oral naltrexone is problematic and leads to extremely high dropout rates, with the occasional exception of treatment in criminal justice and other settings where relapse may be linked to severe adverse consequences [96-98]. This has led to intensive efforts – including NIDA- and NIAAA-funded grants to small businesses – to develop long-acting naltrexone preparations that can be administered as an injection or placed as an implant once per month or less frequently [99, 100].

XR-NTX (Vivitrol®, NTX-containing polylactide-co-glycolide [PLG] biodegradable sterile microspheres suspended in a diluent) is delivered by monthly injection into the muscles of the upper outer quadrant of the buttock. Each vial of microspheres contains 380 mg NTX which are suspended by adding a diluent that comes with the product and shaking for about a minute prior to injection of the full (less dead-space) content of the vial. Plasma concentrations of NTX and 6-beta-naltrexol (its main active metabolite) after a single XR-NTX injection are detectable for at least 30 days. Consistent with this, in human laboratory studies with Vivitrol® and Depotrex®, an essentially complete blockade of opioid agonist effects is seen for 30 days [101, 102]. To maintain blockade beyond 30 days, XR-NTX must be re-administered. Long-term use of NTX and XR-NTX is not associated with tolerance, dependence, addiction or withdrawal on discontinuation. NTX and XR-NTX will, however, precipitate withdrawal in individuals physiologically dependent on opioids and decrease opioid tolerance.

As a consequence of its extended duration of action and assured treatment adherence, XR-NTX may dramatically and favorably alter the limited effectiveness profile associated with orally administered NTX. By ensuring 30-day medication adherence with a single injection, and thereby establishing a ~30 day mu-opioid antagonist blockade, the likelihood of an individual re-establishing opioid dependence during this period is very low. Two clinical trials support efficacy for XR-NTX preparations compared to placebo injections [54, 55].

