9.1.6 Medical Record Release Form

Participants will complete the form(s) as applicable during screening and throughout the study to grant permission to study staff to review inpatient, outpatient, mental health, and substance use treatment clinic records as needed. The purpose of medical record review at the end of study participation is to document information needed to evaluate secondary outcomes. Specifically, study staff will abstract medical record information to corroborate participants' self-report of information including, but not limited to the following: HIV viral load and CD4 count, liver enzymes, hepatitis B and C serologies, CBC, metabolic panel, INR, utilization of HIV primary care, utilization of HIV and addiction treatment services, and opioid overdose events. Records review/abstraction will occur throughout the study (as needed) and up to 52 weeks post-randomization.

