Among the 9 individuals in the pilot study who had opioid use disorder and were unsuppressed at baseline, 6 (17%) of the 36 subsequent viral load values were missing. In the pilot, viral load was measured monthly, increasing the opportunity for missing data, whereas CTN-0067 collects follow-up viral loads only at 12 and 24 weeks and will likely have fewer missing viral loads. The primary outcome analysis will be carried out using the binary repeated measures of viral load (RMVL) framework of Rose et al., a type of time series model. In theory, time series models can accommodate missing data better than non-longitudinal models by using all non-missing data points. However, this approach assumes that missing data are not informative, that is, that missing values are probably similar to corresponding non-missing values with the same set of other predictors. For substance-use trials, missing at random (MAR) is less likely than missing not at random (MNAR) alternative: if data are missing, it is probably because the participant is unsuppressed. So, for the primary analysis, “unsuppressed” will be substituted for missing suppression status values. Since death is at least as undesirable as lack of suppression, “unsuppressed” will be assigned as a status value for visits subsequent to death. A secondary sensitivity analysis will explore the extent to which trial conclusions need to be changed as the missingness assumption approaches MAR.

9.2.3.4 *Dispensing of XR-NTX*

Study medication (XR-NTX) will be provided by the study at no cost to the participant. XR-NTX will be administered in clinic at the Treatment Initiation Visit and at treatment weeks 4, 8, 12, 16 and 20.

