9.9 Long Term Mortality Follow-up

In the future, we will attempt to account for all participants who may have died after the study ends. We will do this by sending participant data to the National Center for Health Statistics' (part of the Centers for Disease Control and Prevention) National Death Index. This is a list of all persons who have died in the U.S. Data, if available, will be abstracted from the Locator Form and other CRFs and may include name, date of birth, sex, race/ethnicity, social security number, state of residence, date of last contact, and date of death. The date and cause of death identified

by the National Death Index will be entered into a secure database at OHSU. Information regarding persons presumed to still be alive in the National Death Index will be destroyed.

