24.2.5.5 Study Specific Risks

XR-NTX blocks the effects of exogenous opioids after administration. After treatment, participants are likely to have reduced tolerance to opioids. Following Vivitrol® treatment, opioid use at the end of a dosing interval or after missing a dose could result in potentially life-threatening opioid intoxication (involving respiratory compromise or arrest, circulatory collapse, etc.) Attempting to overcome the blockade effects of Vivitrol® by administering large amounts of exogenous opioids is associated with potential risk of opioid overdose. Participants in this study will receive an information card that will notify clinicians that they are receiving XR-NTX as part of a research study.

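### The overdose-specific assessments end at week 24, just as blockade from a week-20 injection ends, and the overdose chart data planned to week 52 have no place in sections 15.2, 15.3 or 17.13

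*Combined protocol and SAP*

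**What the plan says.** **The risk.** Section 24.2.5.5 states: "After treatment, participants are likely to have reduced tolerance to opioids". It continues: "Following Vivitrol® treatment, opioid use at the end of a dosing interval or after missing a dose could result in potentially life-threatening opioid intoxication". Section 4.1 relays a published criticism of the earlier Russian trial, that "the study did not adequately assess risk of post-treatment overdose".

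**Dosing and duration.** Section 9.2.3 gives the schedule: "XR-NTX will be administered in clinic at the Treatment Initiation Visit and at treatment weeks 4, 8, 12, 16 and 20". The documents give three durations of effect: 28 days (2.0 Synopsis); "an essentially complete blockade of opioid agonist effects is seen for 30 days" (4.2); and full blockade to 5 weeks, with partial blockade beyond (9.2.3.3).

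**Overdose assessments.** Section 15.2 asks about non-fatal overdose in the previous 4 weeks, at baseline and at week 24 or the end-of-study visit. Section 15.3 covers fatal overdose: "We will collect data on fatal opioid overdoses using medical chart record review at 24 weeks for participants who are lost to follow-up". It adds information from the contacts on the locator form.

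**Charts.** Section 9.1.6 lists opioid overdose among the items to abstract, and says: "Records review/abstraction will occur throughout the study (as needed) and up to 52 weeks post-randomization". The stated purposes are to corroborate self-report and to evaluate secondary outcomes. Overdose is not a secondary outcome in 8.2 or 17.3.

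**Other capture.** Adverse events are followed for 30 days, counted from the last study visit in 23.4 but from the last active treatment visit in 24.2.1. Section 9.9 plans a National Death Index search: "we will attempt to account for all participants who may have died after the study ends".

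**Analysis.** Section 17.13 tabulates adverse and serious adverse events by MedDRA term and arm. It names no overdose table and no period after week 24.

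**The concern.** The protocol names a hazard that rises when blockade wears off and tolerance is low. Its dedicated overdose measurements are timed to the end of the treatment phase. For someone injected at week 20, the week-24 recall looks back over the four weeks in which the drug is blocking. The fatal-overdose chart review is limited to people lost to follow-up, so a participant who attends week 24 and dies of an overdose two weeks later falls outside it.

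At stake is the reading of the safety results. Among participants who take the later injections, a comparison that stops at week 24 sets blocked XR-NTX time against TAU. It could look favourable on overdose partly because the period after the final injection is left out. The record access needed to look further is already in the protocol, but no section commits to using it for this purpose.

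**Working it through.** The plan states no figure to reproduce. The check is a timeline in days from randomization, with visits on their nominal dates.

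**Inputs**
- Last scheduled injection: week 20 = 20 × 7 = day 140 (9.2.3).
- Final visit and both overdose-specific assessments: week 24 = 24 × 7 = day 168 (6.2, 15.2, 15.3).
- Chart abstraction limit: week 52 = 52 × 7 = day 364 (9.1.6).
- Adverse-event capture to 30 days after the last study visit: 168 + 30 = day 198 (23.4).

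**End of blockade and observation after it, for a week-20 dose**

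| Duration (source) | Blockade ends | Day 168 minus end | To day 198 | To day 364 |
|---|---|---|---|---|
| 28 days (2.0) | 140 + 28 = 168 | 0 days | 30 days | 196 days |
| 30 days (4.2) | 140 + 30 = 170 | −2 days | 28 days | 194 days |
| 35 days (9.2.3.3) | 140 + 35 = 175 | −7 days | 23 days | 189 days |

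The week-24 assessments fall at the end of blockade or up to one week before it. Scheduled overdose observation after blockade is 0 days on all three durations. Charts to week 52 would give 189 to 196 days, or 27 to 28 weeks.

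**Adverse-event window.** If the last active treatment visit in 24.2.1 means the week-20 injection visit, capture ends on day 140 + 30 = 170, which is 198 − 170 = 28 days earlier than under 23.4. That leaves at most 170 − 168 = 2 days after blockade. Even on the longer reading, 6.2 schedules no visit after week 24, and 15.1 solicits adverse events at study visits.

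**Recall.** The week-24 question covers weeks 20 to 24, or 4/24 = 17% of the treatment phase. Take a participant whose last injection was at week 8. Blockade ends at week 12 to 13, leaving 11 to 12 unblocked weeks before week 24, of which the instrument reaches the last 4.

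**Route to the safety tables.** Section 15.2 sends a non-fatal overdose that becomes a serious adverse event to the AE/SAE form. Section 19.3.2 exempts only detox admissions, labor and delivery, and planned surgery. Section 19.5, however, sends complications of substance use treatment to study-specific forms and limits AE/SAE hospitalization reports to reasons unrelated to HIV or substance use. Whether non-fatal overdoses reach the 17.13 tables is therefore unclear. Fatal ones do, under 15.3 and 19.5.

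The assessment table in 10.1 was not relied on, because its columns are damaged in the text available.

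**The case against.** A reader might infer that overdose follow-up stops altogether at week 24 and that the week-52 charts are not meant for overdose. The documents do not support that. Section 9.1.6 names overdose events as an abstracted item within the 52-week window. Section 23.4 continues adverse-event follow-up for 30 days after the last visit. The death-index search records date and cause of death, so it can find later fatal overdoses. In-study deaths of people lost to follow-up are the target of 15.3 itself.

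A reader might also infer that the trial observes no time at risk. That holds only for those who take the week-20 dose and then stop. The hazard in 24.2.5.5 includes missed doses, which can occur before week 24. Six-month retention on XR-NTX in the earlier Russian trial is given as 53% (4.2) and 57.9% (4.3), and 5 of 12 pilot participants with opioid use disorder assigned to XR-NTX started within four weeks (4.3). An intention-to-treat arm will contain unblocked time.

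Nor is overdose wholly missing from the by-arm analysis. Fatal events enter the 17.13 tables, as do non-fatal ones reported as serious adverse events. Section 9.4 expects many participants to continue XR-NTX, so week 20 may not be the last injection.

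All of this stands and narrows the point. None of it provides a scheduled overdose assessment after week 24, an overdose chart review for people who completed follow-up, or an analysis of the week-52 data.

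**Conclusion.** The point holds in limited form. The overdose-specific assessments stop at day 168, while blockade from a week-20 dose ends on day 168 to 175. For participants who take that dose and stop, scheduled overdose observation in the named risk period is 0 days. Non-initiators and early stoppers do contribute unblocked time before week 24, but the recall reaches only weeks 20 to 24. The charts in 9.1.6 could supply 27 to 28 weeks more, yet sections 15.2, 15.3 and 17.13 do not connect to them. The adverse-event window adds at most 23 to 30 days without a scheduled contact, and the death index covers deaths only, with no date or analysis attached.

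This rests on nominal visit dates, on the documents' three durations, and on no injection after week 20. For those who continue under 9.4, the 189 to 196 days are a maximum. The primary efficacy analysis is unaffected. The gap is in safety information and should be closed.

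**What to change.** 1. In 15.3, extend the overdose chart review to all randomized participants through week 52, using the abstraction already planned in 9.1.6.
2. In 17.13, add a descriptive by-arm table of fatal and non-fatal opioid overdose and of all deaths, for weeks 0-24 and 24-52. State that treatment after week 24 is not study-provided and that XR-NTX may continue. Report time since last injection only where charts record later injections.
3. In 9.9, run the death-index search from randomization, as a backstop to 15.3.
4. Reconcile 15.2 with 19.5 on whether non-fatal overdoses go on the AE/SAE form, and 23.4 with 24.2.1 on when adverse-event capture ends.
5. State that data to week 24 alone do not adequately assess overdose after the final injection.

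The cost is a week-52 chart review per participant within the existing record release, some extra abstraction of later injections, and the wording above. The week-52 table would be a supplementary report, 52 − 24 = 28 weeks after the last week-24 visit. Charts will miss events treated elsewhere in either arm, and exposure after week 24 will be mixed, so the later period supports description rather than a clean comparison of treatments.

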15.4 Precipitated Withdrawal

For participants assigned to XR-NTX, the study clinician will record the presence or absence of precipitated opioid withdrawal on the XR-NTX Administration (INJ) CRF following each XR-NTX injection.

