9.2.3 Clinic-based Extended-Release Naltrexone (XR-NTX)

9.2.3.1 *XR-NTX Detoxification and Induction (0 - 4 weeks duration, during active treatment phase)*

Following randomization, participants assigned to office-based XR-NTX will undergo detoxification and naltrexone induction in accordance with the package insert and published guidelines [133-136]. Participating HIV providers will be trained to manage outpatient detoxification procedures for participants with mild to moderate anticipated opioid withdrawal severity. Provider training reviews a range of detox options outlined in the Manual of Operating Procedures [137, 138]. Participants failing an induction regimen and those with anticipated severe withdrawal may be referred to local detox facilities for medication-assisted inpatient detoxification.

9.2.3.2 *Active Treatment with XR-NTX (Treatment Initiation through Week 20)*

XR-NTX (4cc, ~380mg of naltrexone base) will be administered *approximately* every four weeks (treatment initiation visit and weeks 4, 8, 12, 16, and 20) for an approximate maximum of 6 doses in the form of Vivitrol®, which will be obtained by NIDA or the NIDA contractor for distribution to the sites. Administration of XR-NTX more frequently will require approval by the Lead Investigators and will be provided on a case-by-case basis. XR-NTX will be administered by intramuscular injection to the buttocks (alternating sides monthly) according to the injection preparation and administration procedures specified in the Vivitrol® product package insert. These procedures are designed to minimize the risk of injection site reactions.

9.2.3.3 *Handling of Missed XR-NTX Doses, Lapses, and Relapses*

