9.3 Ancillary Treatments

Participants who experience withdrawal symptoms or nausea associated with detoxification and induction may be treated with ancillary medications (see guidelines in study Manual of Operating Procedures (MOP)). Depression is also common in opioid-dependent participants and, though not causally related to XR-NTX use, may adversely affect prognosis of naltrexone treatment [140,

141]. Participants who show depressive symptoms may be treated by their HIV clinic providers with antidepressants and/or referred for mental health evaluation and treatment.

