15.0 SAFETY ASSESSMENTS

15.1 Adverse Events, including Serious Adverse Events, and Protocol Deviations

Adverse Events, Serious Adverse Events, and Protocol Deviations will be assessed and documented.

Study staff members will assess for any medical or psychiatric side effects by asking: "How have you been feeling since your last visit?" AEs will be solicited at each study visit but will be recorded at any visit after consent when reported by the participant according to the adverse event reporting definitions and procedures outlined in the protocol.

If a reported AE suggests medical or psychological deterioration, it will be brought to the attention of the study clinician for further evaluation. SAEs will be medically managed, reported, and followed in accordance with applicable regulatory requirements. Safety assessments will be performed at all visits.

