16.4 Concomitant Medications

Participants will be instructed to contact the study clinician at their research site if they plan on taking any concomitant medications (including prescription, over-the-counter, and herbal supplements) during the course of the study. Concomitant medications will also be assessed at screening.

As described in the eligibility criteria, participants will be excluded if there is a need for ongoing opioid analgesic treatment. The study clinician may also exclude any participant taking medications that could interact adversely with study drugs, at his/her clinical discretion.

Study screening and treatment induction procedures (requirement for negative UDS for opioids on day of induction – XR-NTX arm only) are anticipated to greatly decrease the risk of precipitating opioid withdrawal. In the event a participant experiences opioid withdrawal following XR-NTX injection, the study clinician may dispense symptomatic treatments (e.g., oral clonidine, prochlorperazine, ibuprofen, etc.) to alleviate symptoms of opioid withdrawal, according to local SOPs. XR-NTX can also be associated with transient nausea unrelated to opioid withdrawal, typically lasting 2-8 hours. Should participants develop nausea or vomiting during naltrexone induction, this will be treated with oral anti-emetics (e.g., prochlorperazine) as needed.

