19.3.1 Adverse Events

For the purposes of this study, mild (Grade 1) and unrelated Adverse Events will not require reporting in the data system. All adverse events will be tracked on a manual (paper only) Adverse Event Log, regardless of severity, seriousness, relatedness, or expectedness.

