23.4 Site's Role in Eliciting and Reporting Adverse Events

Appropriately qualified and trained study staff will elicit participant reporting of AEs and SAEs at each study visit designated to collect AEs. Adverse events (medical and/or psychiatric) assessment will initiate with participant consent and follow-up will continue through 30 days post last study visit. Study staff will obtain as much information as possible about the reported AE/SAE to complete the AE/SAE forms and will consult with the lead team as warranted.

Standard reporting, within 7 days of the site becoming aware of the event, is required for reportable AEs. Expedited reporting (within 24 hours of their occurrence and/or site's knowledge of the event) is required for reportable SAEs (including death and life-threatening events). Local sites are responsible for reporting SAEs to their IRB, per their IRB's guidelines when operating under an IRB Authorization Agreement.

Site staff is required to enter reportable AEs and SAEs in the Advantage eClinical system. The AE form is used to capture reportable AEs (as defined in the protocol). Additional information may need to be gathered to evaluate serious adverse events and to complete the appropriate CRFs and the summary. This process may include obtaining hospital discharge reports, medical records, autopsy records or any other type of records or information necessary to provide a complete and clear picture of the SAE as well as events preceding and following the SAE. If the SAE is not resolved or stable at the time of the initial report or if new information becomes available after the initial report, follow-up information must be submitted as soon as possible.

Reportable adverse events will be followed until resolution, stabilization or study end. Any serious adverse reactions will be followed until resolution or stabilization even beyond the end of the study.

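### Sections 19.5 and 19.3.2, read literally, can keep withdrawal precipitated by study naltrexone off the AE/SAE forms, so the XR-NTX safety tables may omit it or count it unevenly across sites

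*Combined protocol and SAP*

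**What the plan says.** **The reaction is foreseen.** Section 4.2 states that naltrexone precipitates withdrawal in people who are physically dependent on opioids. Section 9.1.9 does not require abstinence at randomization. Section 9.2.3.1 puts detoxification and naltrexone induction after randomization and adds: "Participants failing an induction regimen and those with anticipated severe withdrawal may be referred to local detox facilities". Section 9.3 provides for symptomatic care: "Participants who experience withdrawal symptoms or nausea associated with detoxification and induction may be treated with ancillary medications". According to 16.4, screening and induction procedures, including a negative opioid urine screen on the day of induction, "are anticipated to greatly decrease the risk of precipitating opioid withdrawal".

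**How it is recorded.** Under 15.4 the clinician "will record the presence or absence of precipitated opioid withdrawal on the XR-NTX Administration (INJ) CRF following each XR-NTX injection". No rule there links that entry to the AE/SAE form.

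**General AE rules.** Section 15.1: "AEs will be solicited at each study visit but will be recorded at any visit after consent when reported by the participant". Section 23.4 says AE "assessment will initiate with participant consent". Section 19.3.1 says that "mild (Grade 1) and unrelated Adverse Events will not require reporting in the data system", and keeps a paper log of all AEs.

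**Exceptions.** Section 19.3.2 lists detox admissions among the events not reported as SAEs; they go on the DTX form. Section 19.5 places events related to HIV complications, substance use treatment or detox admission on study-specific forms, without a second report as an AE or SAE. The hospitalizations it names for AE/SAE forms are those unrelated to HIV or substance use, and it adds deaths. It also says the data still go to the DSMB.

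**Tables.** Section 17.13 summarizes AEs and SAEs by MedDRA term, overall and by arm. It describes no table for the 15.4 item.

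**The concern.** Two sets of rules apply to one reaction and lead to different forms. Under the general rules, withdrawal caused by study naltrexone is a related AE and belongs in the data system. Under 19.5, and under 19.3.2 if the participant is admitted for detox, it can be documented elsewhere and left off the AE/SAE forms. Only those forms feed the tables in 17.13.

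The reaction comes from study naltrexone, so any omission falls on the XR-NTX arm and would make that arm look somewhat better tolerated than it was. If sites read 19.5 differently, the reported frequency would partly reflect coding habits. A clinic deciding whether to adopt XR-NTX would want this figure counted in one way.

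**Working it through.** There is no plan figure to reproduce. The check follows two hypothetical events through the text.

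**Event A: moderate withdrawal after an XR-NTX injection, managed in clinic.**

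1. Section 23.1 defines an AE as any untoward medical occurrence during the trial, so this is an AE.
2. Section 23.6.1 asks whether the drug could reasonably have caused it. The answer is yes, so it is a suspected adverse reaction.
3. Section 19.3.1 exempts only events that are both mild and unrelated. This one is neither, so it should be entered and would appear in the 17.13 tables.
4. Section 19.5 exempts events related to substance use treatment that are captured on a study-specific form. XR-NTX is substance use treatment, and the form named in 15.4 is such a form. Read literally, the event stays there and does not appear in the 17.13 tables.

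Steps 3 and 4 disagree, and no section says which governs.

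**Event B: the same reaction, leading to inpatient detox.**

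1. Section 23.1 counts inpatient hospitalization as serious, so this is an SAE.
2. Section 19.3.2 takes detox admissions out of SAE reporting. It does not separate a planned detoxification from an admission caused by the study drug.
3. Section 19.3.2 then requires all other SAEs to be reported. That does not help if the site classes the admission as a detox admission.
4. Section 19.5 names for AE/SAE forms the hospitalizations unrelated to HIV or substance use, which does not bring this one back.

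**Neighbouring sections.** Section 15.2 says a non-fatal overdose that led to an SAE is also entered on the AE/SAE form, and 15.3 says the same of a fatal opioid overdose. Section 15.4 has no counterpart. Section 19.4, on study-drug toxicity, refers only to the package insert and gives no reporting rule.

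**Size.** The number of events affected would be the number of precipitated-withdrawal events multiplied by the share that sites route away from AE/SAE forms. The documents give neither input and support no range for either, so no figure is offered.

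**The case against.** The best defence is that 19.5 was never meant to cover drug reactions. Its heading concerns the underlying condition and the study population, and drug toxicity has its own section, 19.4. A clinician applying 23.1, 23.6.1 and 19.3.1 would report the event. Section 19.5 can also be read as a rule against double entry only, and the 15.2 rule applies only to overdoses that are already SAEs, so its contrast with 15.4 is modest.

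Much of this stands. Reporting the event as an AE is a reasonable reading and may be the intended one. But the operative words of 19.5 reach substance use treatment, and 19.4 supplies no rule to set against them. The double-entry reading does not help after an injection: the 15.4 form already holds the event, so a rule against entering it twice keeps it off the AE form.

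A reader might go further and infer that withdrawal before a first injection is not captured at all. The documents do not support that:

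- No section states that naltrexone is given before the first injection. Sections 14.1 and 13.6 place study drug induction at the Treatment Initiation Visit, where the first injection is given and 15.4 applies. Section 16.4 mentions nausea separately ("Should participants develop nausea or vomiting during naltrexone induction, this will be treated with oral anti-emetics"), but that does not establish an earlier dose.
- The assessment table in 10.1 lists a Detoxification form and a Naloxone Challenge form, and 12.10 describes a Non-Initiation form. Their fields, and the Manual of Operating Procedures, are not supplied. They may already record such a reaction.
- AEs are solicited from consent onward and logged on paper whatever their severity or cause.

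A reader might also size the gap from the pilot in 4.3, where 5 of 12 OUD participants assigned to XR-NTX started within 4 weeks, leaving 12 − 5 = 7 (7/12 = 58%) without an injection by then. That counts people not injected. It measures neither naltrexone exposure nor withdrawal events, and should not be applied to the 175 in the arm.

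**Conclusion.** The point holds as a reporting conflict and is minor. Sections 19.5 and 19.3.2 allow a known reaction to the study drug to be left off the AE/SAE forms, 19.3.1 implies the opposite, and 15.4 and 17.13 do nothing to settle it. The XR-NTX safety tables can therefore omit the reaction or count it unevenly between sites, and an analyst could not reliably reconstruct each site's routing afterwards.

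This rests on a literal reading of 19.5 and assumes that the unseen Manual does not override it. Whether naltrexone precedes the first injection, and whether the Detoxification or Naloxone Challenge forms already capture a reaction, cannot be determined from the documents. The DSMB still receives the data, so oversight continues. The non-inferiority analysis, sample size and error rate are untouched.

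**What to change.** 1. **19.5 and 19.3.2.** Add: *Withdrawal judged precipitated by study naltrexone, including when it leads to a detox admission, is reported as an AE, or as an SAE if serious.*
2. **15.4.** Add that a recorded event is also captured on the AE/SAE form, and that the rule covers any naltrexone dose given before the first injection, if the Manual allows one.
3. **17.13.** Tabulate participants with at least one precipitated-withdrawal event in two rows: among all randomized to XR-NTX, and among those injected. The first denominator includes people never given naltrexone; the second leaves out anyone never injected. Label both plainly, since neither is exactly a rate among the exposed.

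The cost is a sentence or two in each of three sections, one table and a note to sites. Sites do slightly more data entry, and the reported rate may be less favourable to XR-NTX. Induction procedures do not change.
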